#### 8.5. Time-to-Resolution Definition

In order to derive the time-to-resolution, overlapping or contiguous AESI within a specific category will be collapsed into what will be termed "clustered" AESI. For example, if a subject (without pre-treatment AE) experienced an AE from 01 January to 05 January, another AE (with different PT but within same category) from 06 January to 11 January, and the same AE from 10 January to 12 January, these will be collapsed into one clustered AESI from 01 January to 12 January. Table 11 summarizes key derivation steps for each type of clustered select AEs. Algorithm for collapsing multiple records of adverse event is summarized in section 8.6.

Time-to-resolution of AESI (any grade) for a specific category is defined as the longest time from onset to complete resolution or improvement to the grade at baseline among all clustered AESI in this category experienced by the patient. Events which worsened into Grade 5 events (death) or have a resolution date equal to the date of death are considered unresolved. If a clustered AESI is considered to be unresolved, the resolution date will be censored to the last known date alive. Improvement to the grade at baseline implies that all different AE events in the clustered AESI should at least have improved to the corresponding (that is, with same preferred term) baseline grade. This measure is defined only for subjects who experienced at least one AESI in the specific category.

The time-to-resolution of AESI (Grade 3-5) for a specific category is defined similarly with an onset date corresponding to a Grade 3-5 AESI.

Time-to-resolution of drug-related AESI (any grade or Grade 3-5) is defined similarly but restricted to drug-related AESI.

Time-to-resolution for a specific subcategory is defined similarly but restricted to events of this subcategory.

**Table 11:** Derivation of Clustered AESI

Type of clustered select AE	Derivation
Any grade	Collapse any on-treatment AESI from the same category
Drug-related of any grade	Collapse any on-treatment drug-related AESI from the same category

Type of clustered select AE	Derivation
Grade 3-5	Collapse any on-treatment AESI from the same
	category.
	Resolution will be based on the onset date of the earliest
	Grade 3-5 records (if no Grade 3-5 record, clustered
	AESI is excluded)
Drug-related of Grade 3-5	Collapse any on-treatment drug-related AESI from the
	same category. Resolution will be based on the onset
	date of the earliest Grade 3-5 record (if no Grade 3-5
	record, clustered AESI is excluded)

Abbreviations: AE=adverse event; AESI=adverse event of special interest.

### **8.6.** Multiple Adverse Events

The algorithm for collapsing multiple records of select adverse event is using the following conventions. For each patient and specified category, the corresponding adverse event records will be collapsed when:

Multiple adverse event records have the same onset date.

The onset date of an event record is either the same day or 1 day later than the resolution date of a preceding event record (contiguous events).

The onset date of an event record is after the onset date and prior to or on the resolution date of a preceding event record (overlapping events).

### 8.7. Other Data Handling Rules

Missing data will not be imputed in the patient level listings. The listings will only present the data recorded on the original CRF.

If an AE has a completely missing onset date, the AE will be included in the AE summary tables. A medication with a completely missing start date is considered a prior medication. A medication with a completely missing stop date is considered a concomitant medication.

If an adverse event or a medication has a partial missing start or stop date, the following rules will be used to determine whether it is an AE for the AE summary tables, or a prior or concomitant medication.

Table 12. Partial Date Imputation Rule for AE or Medication

Partial Missing Start or	Derived Start Date	Imputed Stop Date
Stop Date		
Missing month and day,		
and the year is present	date if the year is the same as the	year
	year of first dose date	
Missing day, but year and		Last day of that month
month are present	dose date if the year and month are	

Partial Missing Start or Stop Date	Derived Start Date	Imputed Stop Date
	the same as the year and month of first dose date	
Missing month, but year and day are present	Missing month derived as January or same as first dose month if the year is same as the year of first dose.	Missing month imputed as December

The above rule is also used for determining the cycles of adverse events and concomitant medications.

The derived date is only used for determining AEs, cycle of adverse events and concomitant medications. The collected partial dates will be reported in the listings.

For the medical history, prior surgery, prior radiotherapy, and prior systemic cancer therapies:

- Missing day and month January 1 will be assigned to the missing fields.
- Missing month only Treat day as missing and replace both month and day according to the above procedure.
- Missing day only Assign first of the month to the missing day.

Partially missing stop dates for the types of data listed above will be imputed as:

- year is missing, no imputation. Date left missing.
- month is missing and year is prior to year of first dose of study medication- impute 'December'.
- month is missing and year the same as the year of the first dose of study medication impute same month as in start date of study medication.
- day is missing, impute 'last date of that month'. If results in a date ≥ the date of the first dose of study medication impute day as the day prior to the first dose of study medication.

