## Statistical Analysis Plan

Table 4: Partial Date Imputation for TEAE Determination

Partial Missing Start or Stop Date	Derived Start Date	Imputed Stop Date
Missing month and day, and the year is present	January 1 of that year or first dose date if the year is the same as the year of first dose date	December 31 of that year
Missing day, but year and month are present	First day of that month or first dose date if the year and month are the same as the year and month of first dose date	Last day of that month
Missing month, but year and day are present	Missing month derived as January or same as first dose month if the year is same as the year of first dose.	Missing month imputed as December

The above rule is also used for determining the cycles of adverse events and concomitant medications.

The derived date is only used for determining TEAEs, cycle of adverse events and concomitant medications. The collected partial dates will be reported in the listings.

Sponsor: Taiho Oncology, Inc. Protocol: TPU-TAS-120-101

Version: 3.3, Phase 1 Dose Escalation Only

Statistical Analysis Plan

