#### 6.5.2.5. Adverse Events

An adverse event (AE) is any untoward medical condition that occurs in a patient while participating in this clinical study. Adverse events will be coded according to the Medical Dictionary for Regulatory Activities (MedDRA 18.1) terminology and the severity of the toxicities will be graded according to the NCI CTCAE, v4.03, where applicable.

Adverse Events that occur from the initiation of TAS-120 medication administration to 30 days after the last dose of study medication, and do not necessarily have a causal relationship to the use of the study medication will be summarized.

Number of patients with AEs will be presented by system organ class in the overall column in decreasing order. Within each system organ class, the number of patients with AEs will be displayed by preferred term (PT) in descending order.

The following adverse event summary tables will be generated:

1) An overall summary with the number and percentage of patients reporting AEs, serious AEs, grade 3 or higher AEs, treatment-related AEs, AEs leading to study treatment (TAS-120) discontinuation and AEs with outcome of deaths.

In the summary, a patient is counted once at the system organ class and once at each preferred term within the system organ class. Additional summary by system organ class,

preferred term and grade (including Total and >= grade 3 categories) will also be generated.

- 2) Study-treatment-related AEs overall and by system organ class and preferred term. Additional summary by system organ class, preferred term and grade (including Total and >= grade 3 categories) will also be generated.
  - All those AEs with relationship to TAS-120 marked as "Related" or missing will be reported in the table.
- 3) AEs by highest grade (worse severity) overall and by system organ class and preferred term.
  - In the summary, a patient is counted once at the highest grade for which the event occurred in the system organ class and the highest grade for each unique preferred term within that system organ class. Therefore, patients may only contribute once to each preferred term and once to each system organ class. The missing severity grade will be reported in a separate category.
- 4) Grade 3 or higher AEs, overall and by system organ class and preferred term
- 5) Study-treatment related AEs by grade (severity), overall and by system organ class and preferred term

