#### 8. DEFINITIONS AND CONVENTIONS FOR DATA HANDLING

#### 8.1. Baseline Period

Baseline evaluations or events are defined as evaluations or events that occur before the date and time of first dose of study treatment.

If the onset time of event or evaluation time or dosing time is missing or not collected, the following definitions will be applied:

- Pre-treatment AEs will be defined as AEs with an onset date prior to but not including the day of the first dose of study treatment
- Baseline evaluations (laboratory tests, vital signs) will be defined as evaluations with a date on or prior to the day of first dose of study treatment

If there are multiple valid assessments, the assessment that is closest to day (and time if collected) prior to the first dose of study treatment will be used as the baseline in the analyses. If multiple assessments are collected at the same date (and time if collected), the assessment with the latest database entry date (and time if collected) will considered as baseline.

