# 7.7. Other Data Handling Rules

Missing data will not be imputed in the patient level listings. The listings will only present the data recorded on the original CRF.

If an AE has a completely missing onset date, then the AE will be considered a TEAE. A medication with a completely missing start date is considered a prior medication. A medication with a completely missing stop date is considered a concomitant medication.

Taiho Oncology, Inc. Statistical Analysis Plan (Phase 2) – Protocol TPU-TAS120-101

15 October 2020

If an adverse event or a medication has a partial missing start or stop date, the following rules will be used to determine whether it is an AE or a TEAE, or a prior or concomitant medication.

Table 14. Partial Date Imputation Rule for TEAE or Medication

Partial Missing Start or	Derived Start Date	Imputed Stop Date	
Stop Date			
Missing month and day,	January 1 of that year or first dose	December 31 of that	
and the year is present	date if the year is the same as the	year	
	year of first dose date		
Missing day, but year and	First day of that month or first	Last day of that month	
month are present	dose date if the year and month are		
	the same as the year and month of		
	first dose date		
Missing month, but year	Missing month derived as January	Missing month imputed	
and day are present	or same as first dose month if the	as December	
	year is same as the year of first		
	dose.		

The rule above in Table 14 is also used for determining the cycles of adverse events and concomitant medications.

The derived date is only used for determining TEAEs, cycle of adverse events and concomitant medications. The collected partial dates will be reported in the listings.

For the medical history, prior surgery, prior radiotherapy, and prior systemic cancer therapies:

- Missing day and month January 1 will be assigned to the missing fields.
- Missing month only Treat day as missing and replace both month and day according to the above procedure.
- Missing day only Assign first of the month to the missing day.

Partially missing stop dates for the types of data listed above will be imputed as:

- year is missing, no imputation. Date left missing.
- month is missing and year is prior to year of first dose of study medication- impute 'December'.
- month is missing and year the same as the year of the first dose of study medication impute same month as in start date of study medication.

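### An AE missing only its onset month can be dated before first dose and left out of the AE tables, although the same AE with less date information would be counted

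*SAP*

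**What the plan says.** Expansion SAP 8.7 says of partially dated records that its "rules will be used to determine whether it is an AE for the AE summary tables, or a prior or concomitant medication". Table 12 has three rows for start dates.

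- **Month and day missing.** The Expansion row is broken in the extracted text. The same row is intact in Dose Escalation Table 4 and gives "January 1 of that year or first dose date if the year is the same as the year of first dose date".
- **Day missing.** The first of the month is used, or the first dose date if year and month match those of first dose.
- **Month missing, day known (row 3).** "Missing month derived as January or same as first dose month if the year is same as the year of first dose".

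A date that is missing altogether is settled outright: "If an AE has a completely missing onset date, the AE will be included in the AE summary tables". Phase 2 SAP 7.7 and Dose Escalation SAP 7.3 do the same by calling such an event treatment-emergent. Row 3 recurs in Phase 2 Table 14 ("Missing month derived as January", or the first-dose month in the same year) and in Dose Escalation Table 4.

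The derived date is then classified. Expansion SAP 8.1 states: "Pre-treatment AEs will be defined as AEs with an onset date prior to but not including the day of the first dose". Section 6.5.2.5 summarises "Adverse Events that occur from the initiation of TAS-120 medication administration to 30 days after the last dose of study medication". The derived date also sets the AE's cycle. Listings keep the partial date as collected.

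**The concern.** The other rows resolve doubt towards counting. When the known parts of the date fit the first-dose year or month, they fall back on the first dose date, and a missing date is counted. Row 3 alone has no such fallback. It joins a recorded day to a borrowed month, and the result can precede treatment even though the true onset followed it. A record with more date information can then be excluded while the same event with less is included.

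At stake is the classification of a few AEs in descriptive safety tables and their assignment to a cycle. A rule for uncertain AE dates in a single-arm safety summary should not be able to remove an event that may well be on treatment. A smaller, separate gap runs the other way: no AE start-date row checks a known stop date. An AE with onset in the first-dose month, day missing, and a stop date before dosing still takes the first dose date and is counted.

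**Working it through.** The plan gives no figure on this point, so there is none to reproduce. The check applies the table literally.

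**Inputs.** The three start-date rows and the missing-onset rule (Expansion SAP 8.7, with the broken row completed from Dose Escalation SAP 7.3); the pre-treatment definition (8.1); the summary window (6.5.2.5); AE collection from consent (Expansion SAP Table 1); consent up to 28 days before first dose (Expansion SAP 5.1).

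**Condition.** Let first dose be day D0, month M0, year Y0, and let the AE have day d, month unknown, year Y0. Row 3 derives (Y0, M0, d), which is before first dose exactly when d < D0. If the AE year is later than Y0, January with the recorded day still falls after first dose and the AE is counted.

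**Worked example.** First dose 20 March 2018, true onset 10 May 2018.

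| What is recorded | Derived onset | AE tables |
|---|---|---|
| Full date | 10 May | counted |
| Day missing | 1 May | counted |
| Month missing | 10 March | left out |
| Month and day missing | 20 March | counted |
| Nothing | none | counted |

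**How often row 3 misdates, among AEs missing only their month in the first-dose year.** These shares are illustrative. The assumed distributions are not in the documents.

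1. Every first-dose date in 2018, paired with every on-treatment onset to the end of that year: 29,277 / 66,795 = 43.8% derived before first dose. With month and day both missing, the count is 0.
2. The same enumeration by day of first dose: day 1, 0%; day 10, 26%; day 20, 58%; day 31, 98%.
3. With onsets limited to first dose through last dose + 30 days, a simulation of 60,000 records per treatment length gave 45.6%, 45.1%, 44.7% and 44.1% for 60, 120, 180 and 270 days. Exact enumeration over one year of first-dose dates agrees: 13,035 / 28,845 = 45.2%, 19,608 / 43,575 = 45.0%, 24,468 / 54,705 = 44.7%, 28,620 / 64,650 = 44.3%.
4. In the other direction, true pre-dose onsets derived on or after first dose: consent 21 days before dosing, 2,541 / 7,434 = 34.2%; 28 days, 4,466 / 9,814 = 45.5%.

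**With a floor at first dose.** The count in step 1 falls from 29,277 to 0. The price is on the pre-dose side: an AE of this type that truly preceded dosing is counted whenever no stop date shows that it ended before first dose. Under the present rule, 34% of them are counted (21-day consent).

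**The case against.** The strongest reply is rarity. The trigger needs a known day and year with an unknown month, in the first-dose calendar year, with a day earlier than the first-dose day. Protocol 11.1.1 requires onset and resolution dates for every AE, entered within 10 business days. SAEs are reported within 24 hours (11.1.2), and entries are monitored and queried (14.4). The Dose Escalation SAP's own example of a partial date (17.2.5.3) lacks the day, not the month. This stands: the documents give no count of such records, and there may be none.

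It follows that a reader might infer that on-treatment events will be lost from the AE, SAE and AESI tables. The documents support only that they could be, and for SAEs it is least likely. Nor does the rule err in one direction only, as the 34% shows.

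A reader might also take one favourable case as typical. With first dose on 20 June 2019 and onset day 3, the candidates run from 3 June to 3 December, and 6 of 7 are on treatment. That needs a last dose on or after 3 November, 137 days counting both ends. With 60 days of treatment the window closes on 17 September and the count is 3 of 4.

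The convention in 8.7 for medical history, "Treat day as missing and replace both month and day according to the above procedure", looks like a ready repair. It is not: that procedure assigns January 1, which would make nearly all same-year AEs pre-treatment. Rewriting row 3 as a whole would also move medication start dates, because the table governs prior and concomitant status too.

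Finally, Dose Escalation Table 2A collects AEs from first dose, so the pre-dose counts and the stop-date gap do not apply there. The missing floor does.

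None of this changes what row 3 does when it is triggered, and no other text in the SAPs overrides it.

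**Conclusion.** The rule is wrong as written, but minor. In all three SAPs, an AE missing only its month in the first-dose year is derived as pre-treatment whenever its recorded day is earlier than the first-dose day, and could then be left out of the AE summary tables. The same AE with less date information would be counted.

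The 44-46% figure is conditional on such a record existing. It rests on uniform first-dose and onset dates, consent 21 days before dosing and treatment of 2 to 9 months. The narrow range averages over a spread from 0% to about 98% by day of first dose, so it should be read as illustration, not as an expected loss. The documents do not support a claim of material under-reporting of safety, and no efficacy analysis or decision rule is touched. Low priority.

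**What to change.** 1. In row 3 of Expansion Table 12, Phase 2 Table 14 and Dose Escalation Table 4, for AE onset only: if the derived date is before the first dose date, set it to the first dose date. In the Expansion and Phase 2 SAPs add the exception that a known stop date before first dose makes the AE pre-treatment. Leave the medication rules unchanged.
2. Separately, in the Expansion and Phase 2 SAPs, where AEs are collected from consent, apply the same stop-date check to the other AE start-date rows and to the rule for a completely missing onset. In Dose Escalation, where AEs are collected from first dose, the floor alone is enough.

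The cost is a line or two of SAP text and one derivation in each SAP, with no new data. The downside is that a few pre-dose AEs with no informative stop date may be counted as on-treatment, and floored events are assigned to Cycle 1. A count of AE records with only the month missing would show whether any table changes.

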# 1. LIST OF ABBREVIATIONS AND DEFINITIONS OF TERMS

Abbreviation	Term
AE	Adverse event
ALT	Alanine aminotransferase
AST	Aspartate aminotransferase
ATP	Adenosine triphosphate
BUN	Blood urea nitrogen
CCA	Cholangiocarcinoma
Ccr	Calculated creatinine clearance
CI	Confidence interval
CK	Creatine kinase
CK-MB	Creatine kinase (isoform heart muscle)
CR	Complete response
CSF	Cerebrospinal fluid
CTCAE	Common Terminology Criteria for Adverse Events
ctDNA	Circulating tumor DNA
CYP	Cytochrome P450
DCR	Disease control rate
DOR	Duration of response
eCCA	Extra-hepatic cholangiocarcinoma
ECG	Electrocardiogram
ECOG	Eastern Cooperative Oncology Group
EOT	End-of-treatment
EP	Early progression
EPR	Early progression rate
FFPE	Formalin fixed paraffin embedded
FGF	Fibroblast growth factor
FGFR	Fibroblast growth factor receptor
GCP	Good Clinical Practice
iCCA	Intra-hepatic cholangiocarcinoma
ICH	International Council for Harmonisation
INR	International normalized ratio
MedDRA	Medical Dictionary for Regulatory Activities
ms	Milliseconds
MTD	Maximum tolerated dose
NCI	National Cancer Institute
PFS	Progression-free survival
PK	Pharmacokinetic(s)
PR	Partial response

Abbreviation	Term
PROs	Patient-Reported Outcomes
PT	Preferred term
QD	Once daily (continuous) dosing
QTcF	Fridericia's corrected QT interval
RECIST	Response Evaluation Criteria in Solid Tumors
RP2D	Recommended Phase 2 dose
SAE	Serious adverse event
SAP	Statistical Analysis Plan
SD	Stable disease
SOC	System Organ Class
WHO	World Health Organization
WOCBP	Women of child-bearing potential

# 2. INTRODUCTION

The purpose of this statistical analysis plan (SAP) is to describe the planned analyses and data displays to be included in the Clinical Study Report (CSR) for the Phase 2 portion of Protocol TPU-TAS120-101.

Cholangiocarcinoma (CCA), a bile duct cancer, is a rare tumor that arises from the malignant transformation of epithelial cells of the bile ducts. It is typically classified as either intrahepatic (iCCA) or extrahepatic (eCCA). Intrahepatic cholangiocarcinoma develops in the smaller bile ducts inside the liver and is the least common form of the disease (approximately 10%), whereas eCCA includes cancers in the peri-hilar (also known as Klatskin tumor) and distal bile duct area and is most common (approximately 90%).

Fibroblast growth factor/fibroblast growth factor receptor aberrations are a reported genetic modification in CCA. In iCCA, FGFR2 gene fusions which are present in an estimated 10% to 20% of patients, 1,2,3 have been identified as an early driver of oncogenic events. Therefore, inhibiting the FGFR pathway in patients with iCCA is a plausible therapeutic strategy for appropriately selected patients with this disease.

TAS-120 (Futibatinib) is a novel selective and irreversible small molecule FGFR inhibitor that equally inhibited all 4 subtypes of FGFR and showed high selectivity for FGFR when tested against a panel of 296 kinases, as in preclinical studies. During the Phase 1 Dose Escalation part of this study, dose levels of 4, 8, 16, 20 and 24 mg QD were evaluated, where 24 mg was determined as the DLT dose level, and 20 mg QD was determined as the maximum tolerated dose (MTD) and RP2D. The Phase 1 Expansion part of the study included a total of 8 treatment groups enrolling different patient populations, including a group of patients with iCCA. The Phase 2 portion of the study is to confirm and assess the efficacy and safety of TAS-120 on patients who have been diagnosed with iCCA harboring *FGFR2* gene fusions or other *FGFR2* rearrangements.

